6.2.2 Formulation, Appearance, Packaging, and Labeling

The device will be manufactured by **National Flag/SBI**. The device will come as a re-useable frame with disposable plastic torso drape. The frame and hand and instrument ports can be cleaned with an antiviral wipe. Hospital grade suction tubing and a disposable torso drape will be provided with each device. Device labeling will include a unique identifier number on each device, clear indicators for orienting the device appropriately around the patient's head and clear markers for placement of suction tubing and the drape for sealing the distal portion of the containment device over the patient's torso. The device will come with a laminated quick-guide card with pictorial and written instructions for use as a quick reference. There will also be a laminated quick reference card for proper removal and cleaning of the device with an antiviral wipe, proper disposal of suction tubing and disposal of the torso drape.

6.2.3 Product Storage and Stability

The frame of the device will be stored in the designated storage area of the study site when not in use. Unused disposable suction tubing and torso draping will be stored along with the device in the designated units. The products are inert without moving parts or electronic components and will be stable for the duration of the study.

6.2.4 Device Preparation, Use, Removal and Cleaning

Device Assembly: The biocontainment device should be brought into the room prior to the procedure. Additional materials needed include the torso drape and the suction tubing (one or two tubing packets will be required depending on distance from device to wall suction).

The patient should be in position and secured properly per site protocol (i.e. with a safety strap with arms and legs appropriately positioned per protocol for procedures on an operating room table). Once this has occurred, the patient should be fully supine with the bed fully level at 0-degrees. The patient's head and the foam headrest should be gently lifted and the biocontainment device base slid under the foam headrest such that the base is centered on the operating room table and squarely on the "head" portion of the operating room table. The primary operator holds the device in place, and secures the front (head side) safety strap to the head of the bed. The left and right straps should then be secured on each side of the bed. Once the biocontainment device is secured, the torso drape should be applied and secured around the patient's torso, leaving small air holes around the patient's arms and the side of the device. To simulate use of the suction, the suction tubing should be secured to the suction port on top of the device on one end and the wall suction nozzle on the other end and the wall suction should be turned on.

Device Use: The anesthesia team should then ensure they have all equipment needed for the airway procedure readily available. The user team should then proceed with airway management technique deemed medically appropriate by the attending anesthesiologist. Note, the ventilator tubing should come out the open torso side under the torso drape. Ensure that air vents around the arms remain open during this time to pull clean air into the biocontainment device. All airway procedure related equipment can be removed during this time.

Device Removal: Following completion of procedure, the suction tubing should be disconnected from the wall and then from the device and disposed of in biohazard waste. The torso drape should be removed carefully and disposed of in biohazard waste. With two people and the patient flat at 0-degrees, the first user should hold the biocontainment device in place while the second person removes the safety strap from around the operating room table. A second member of the procedure team should gently hold the patient's head and the foam headrest, as per standard protocol for adjusting a sedated patient's head, and the first person should gently slide the device out from underneath the patient's head. The device should be placed gently out of the way for cleaning and storage.

Device Cleaning: Wearing gloves, the outside of the biocontainment device should be wiped clean with an antiviral cleaning wipe (bleach or peroxide based). The nylon strap should also be fully wiped down, rolled up and secured in a loop. Attention should be given to carefully wiping down the external layers of the hand and instrument ports. Following cleaning of the outside of the box, an antiviral wipe should then be used to carefully clean the inside of the box paying special attention to clean both layers of the inner aspect of the hand and instrument septums. The device should be allowed to air dry prior to storage and re-use.

Device Storage: See [Section 6.2.3](#) “Product Storage and Stability” above.

6.3 Measures to Minimize Bias: Randomization and Blinding

Randomization will be done to assign patients to intubation with or without the biocontainment device in a 2:1 fashion. This will allow for analysis of patient-related intubation factors as well as user-related intubation factors as part of the feasibility analysis. Blinding is not possible with this study as all users and patients will be aware of the presence of the device intervention. To help minimize bias in the data analysis, results of all data analysis will be assessed by a neutral, third-party with expertise in statistical analysis.

6.4 Study Intervention Compliance

Use of the device will be assessed based on review of videos of the procedures, completion of quality use surveys by user subjects, and completion of the surveys by patient subjects. Each device will have a unique identifier and will be assigned to a specific attending anesthesiologist. The unique device identifier and corresponding attending anesthesiologist for each device will be recorded electronically with each quality use survey. A device use log will be established electronically from this data. If a device needs to be replaced, this will be noted in the electronic log and the new device unique ID number will be added to the electronic device record. Due to constraints entering the hospital at this time by research personnel, completeness of the electronic device logs will be assessed every other week for the duration of the study.

6.5 Concomitant Therapy

User subjects will continue to utilize standard PPE for intubation in the operating room as per hospital policy.

7 STUDY INTERVENTION DISCONTINUATION AND PARTICIPANT DISCONTINUATION/WITHDRAWAL

7.1 Discontinuation of Study Intervention

Discontinuation from active participation using the study device does not mean discontinuation from the study, and remaining study questionnaires not yet completed at the time of discontinuation should be completed as indicated by the study protocol. Discontinuation of device use would occur if the subject user is unable to perform the airway procedure with the device in place. If a clinically significant finding is identified (including, but not limited to changes from baseline) after enrollment, the investigator or qualified designee will determine if any change in participant management is needed. Any new clinically relevant finding will be reported as an adverse event (AE) or ADE.

The data to be collected at the time of study intervention discontinuation will include the following:

- Completion of remaining study questionnaires, collection of patient clinical data and data regarding the intubation procedure from the medical record.

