2.3 Risk/Benefit Assessment

2.3.1 Known Potential Risks

Immediate Risks: There is still a risk of droplet or aerosol exposure to infectious agents, such as SARS-CoV2 (the virus causing COVID-19) with this device. This device does not eliminate that risk and does not replace current CDC guidelines for PPE during an aerosol generating procedure, proper donning, and doffing of PPE and hand hygiene. This device is intended for use *in addition to* recommended PPE during an aerosol generating procedure. Additional bench testing is ongoing to assess the efficacy of the device in containing aerosol and limiting aerosol escape.

There is a risk of device failure due to improper set-up or use of the device. There may be an increase in cognitive burden as a result of introduction of a new form of PPE which has been suggested previously as a source of risk in aerosol generating procedures¹². The weight of the device is **9 lbs** and there is minimal risk of

injury to the user or the patient during setup and use with the device. All training material (written and audiovisual) must be reviewed and the initial survey completed prior to initiating use of the device.

There may be some variability in user comfort performing an intubation with this device. Based on our simulations and completion of the necessary training, there is likely to be minimal risk of a qualified user having device-related issues with intubation. In the event that the user feels the device is impairing their ability to safely intubate the patient, the device can be quickly removed by releasing the safety strap connectors and taking the device off the bed and proceeding to intubate without the barrier in place.

There is a risk of contamination from the device during removal of the device from the patient. PPE should be worn during removal and cleaning/disposal of the device.

There is a small risk of claustrophobia or anxiety for those patients in the device. This is a likely to be a minimal risk and this will be assessed as part of this study. All patients will be monitored while in the device and if they request to be taken out of the device or display signs of increasing anxiety/claustrophobia, the device will be removed.

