3 STUDY OBJECTIVES AND ENDPOINTS

The objectives of this study are to evaluate efficacy of training and use by frontline healthcare workers of a biocontainment system that provides additional protection during aerosol-generating procedures with COVID-19 patients. The primary objectives of this study are: 1) Assess changes in airway procedure times with and without the biocontainment device as a function of repeated utilization and as a function of patient-associated airway factors (Mallampati score, hyomental distance, neck mobility, BMI) and user-associated airway factors (experience of user, airway device used, induction sequence) and 2) Assess adverse events, adverse device events associated with biocontainment device use. Secondary objectives include: 1) Assess the subject's comfort with using the biocontainment device, 2) Assess for additional healthcare and cognitive burden imposed by the device. 3) Survey of patient's post-procedure on experience being inside the device. Exploratory objective includes gathering specific feedback regarding possible design modifications for further iterations and design improvements with the engineering team.

OBJECTIVES	ENDPOINTS	JUSTIFICATION FOR ENDPOINTS
Primary		

 1. Assess changes in airway procedure times with and without the biocontainment device as a function of repeated utilization and as a function of patient-associated airway factors (Mallampati score, hyomental distance, neck mobility, BMI) and user-associated airway factors (experience of user, airway device used, induction sequence). 2. Assess adverse events, adverse device events associated with using the biocontainment device. 	
 1. Measuring the time for performing an airway procedure with the biocontainment device when accounting for patient and user-specific factors. Sub-analysis, based on user experience level. 2. Quantifying the number of AEs or ADEs over time to assess device safety. Breakdown of AEs/ADEs as a function of time and by user subject. 	These endpoints were chosen to assess the safety and efficacy of biocontainment device use over time. This will help assess the viability of the device as an additional layer of protection for aerosol-generating procedures.
Secondary		

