7.2 Participant Discontinuation/Withdrawal from the Study

Participants are free to withdraw from participation in the study at any time upon request.

An investigator may discontinue or withdraw a user subject from the study for the following reasons:

- Significant biocontainment device use non-compliance
- If any clinical adverse event (AE) or ADE, or other medical condition or situation occurs such that continued participation in the study would not be in the best interest of the participant
- If the participant meets an exclusion criterion (either newly developed or not previously recognized) that precludes further study participation
- Participant unable to participate with device use for > 2 weeks.

An investigator may discontinue or withdraw a patient subject from the study for the following reasons:

- If any clinical adverse event (AE) or ADE, or other medical condition or situation occurs such that continued participation in the study would not be in the best interest of the participant
- If the participant meets an exclusion criterion (either newly developed or not previously recognized) that precludes further study participation

The reason for participant discontinuation or withdrawal from the study will be recorded on the Study Withdrawal Case Report Form (CRF). Patient subjects who sign the informed consent form and are randomized to use the biocontainment device but do not utilize the biocontainment device may be replaced. Patient subjects who sign the informed consent form and are randomized and use the biocontainment device, and subsequently withdraw, or are withdrawn or discontinued from the study, will be replaced.

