9 STATISTICAL CONSIDERATIONS

9.1 *Statistical Hypotheses*

We hypothesize that the biocontainment device will be a safe and effective option for performing airway procedures in patients while also providing additional protection during an aerosol generating procedure.

Primary Efficacy Endpoints:

1. We hypothesize that the time to perform an airway procedure with the biocontainment device will be equivalent to time for airway procedure without the biocontainment device. Alternatively, there will be prolonged airway procedures times with the device. This endpoint will be analyzed every two weeks.
2. We anticipate that the number of AEs or ADEs will be low and will also decrease over time. This endpoint will be analyzed on a weekly basis.

Secondary Efficacy Endpoints:

1. We hypothesize that the median Likert ratings for User subject device comfort will be weighted toward “strongly agree”. Alternatively, we will see ratings favoring “neutral” or “disagree” for user subject device comfort.
2. We hypothesize that the median Likert ratings for User subject additional healthcare burden comfort will be weighted toward “strongly disagree”. Alternatively, we will see ratings favoring “neutral” or “agree” on increased healthcare burden.
3. The median Likert ratings for the Patient Experience survey will be weighted toward minimal patient discomfort or anxiety. Alternatively, we will see ratings favoring increased patient discomfort or anxiety inside the device.
3. We anticipate that the median Likert ratings of the patient experience post-survey will indicate overall good user comfort and low levels of anxiety or claustrophobia in the device.

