9.3 Populations for Analyses

For this study, a per-protocol analysis dataset will be obtained. Participants (user and patient subjects) who complied with the protocol will be used to create a dataset. This population for analyses will in effect allow us to analyze outcomes related to the advantages and disadvantages of the protective device of interest. For example, the number of proceduralists who utilized the protective device, overall device utilization and perceived comfort level, added healthcare burden and training level with the device.

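### If users leave device use because procedures fail in it, the repeated-use results can improve without learning; Section 7.1 is unclear on this and the time model in 9.4.2 has no user term

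*Combined protocol and SAP*

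**What the plan says.** **Stopping and withdrawal.** Section 7.1 opens with "Discontinuation from active participation using the study device does not mean discontinuation from the study" and continues: "Discontinuation of device use would occur if the subject user is unable to perform the airway procedure with the device in place". Section 7.2 introduces its user list with "An investigator may discontinue or withdraw a user subject from the study for the following reasons". The reasons include significant non-compliance with device use, more than two weeks without being able to take part in device use, and a clause that begins "If any clinical adverse event (AE) or ADE, or other medical condition or situation occurs", which applies only where continuing would not be in the participant's best interest. Section 8.3.2.3 lists difficulty intubating in the device, and having to take it off, as expected adverse events. The event that may end device use is therefore also counted in a primary endpoint.

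**Results that depend on repeated use.** Primary objective 1 in Section 3 concerns procedure times "with and without the biocontainment device as a function of repeated utilization". Section 9.1 adds: "We anticipate that the number of AEs or ADEs will be low and will also decrease over time". Section 2.3.3 also aims to find how many uses are needed for proficiency.

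**Analysis.** The Section 9.4.2 time model has user experience, number of prior uses and patient factors as covariates, but no term for the individual user. Section 9.3 defines a per-protocol set: "Participants (user and patient subjects) who complied with the protocol will be used to create a dataset". Section 3 promises a breakdown of events by time and by user. No section says how a user's exit is handled in either trend.

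**The concern.** A learning curve compares early with late uses. If the users who struggle are the ones who leave, early uses represent all users and late uses represent those who remain. The pooled slope on prior uses then mixes change within users with change in who is contributing. The same applies to the event rate by use number.

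At stake are the repeated-use part of primary objective 1, the expectation in 9.1 that events will fall, and the proficiency goal. A decline read as learning would suggest that a few uses bring users up to standard, when the users who did not get there had simply stopped contributing. Pooled comfort and burden ratings have a related weakness, because users who continue supply more of them.

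**Working it through.** The documents give no figure for failure rates, user exit or either trend, so there is no stated result to reproduce. The failure rates below are assumptions.

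**Inputs from the documents.** 100 procedures with the device (Section 1.3); 15 to 20 users (Section 5.5). Uses per user: 100/15 = 6.7, or about 7; 100/20 = 5.

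**1. Event rate by use number, no learning, user stops after a first failure.** Let a share w of users fail with probability pH at every use and the rest with probability pL. The failure rate among users still contributing at use k is

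[w·pH·(1−pH)^(k−1) + (1−w)·pL·(1−pL)^(k−1)] / [w·(1−pH)^(k−1) + (1−w)·(1−pL)^(k−1)].

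With w = 1/3, pH = 0.20 and pL = 0.02:
- Use 1: 0.20/3 + 2 × 0.02/3 = 8.0%.
- Use 7: 0.8^6 = 0.262 and 0.98^6 = 0.886, so the weights are 0.0874 and 0.5906. The rate is (0.2 × 0.0874 + 0.02 × 0.5906)/(0.0874 + 0.5906) = 0.0293/0.6780 = 4.3%.

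| pH / pL | Use 1 | Use 7 |
|---|---|---|
| 10% / 2% | 4.7% | 3.8% |
| 20% / 2% | 8.0% | 4.3% |
| 30% / 2% | 11.3% | 3.7% |

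In counts this is small. With 15 users in the middle row, it is 15 × 0.080 = 1.2 expected failures at use 1. At use 7, 15 × 0.678 = 10.2 users remain and 10.2 × 0.043 = 0.44 failures are expected. If each use gave one rating, the failure-prone third would supply 23% of ratings instead of 33%. That assumes one survey per use, whereas Sections 1.3 and 8.1 make it daily and 8.2 makes it per use.

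**2. Simulation of both trends, no learning.** The simulation used 100 device uses, 15 users and 4,000 runs per setting. Failure risk varied between users (beta distribution, mean 5% or 10%, moderate or wide spread). On log time the user SD was 0.25 and the residual SD 0.4. Cases of a user who stopped passed to those remaining.

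| Setting | Event rate, first half of uses | Second half |
|---|---|---|
| No stopping, mean 10% | 10.0% | 10.0% |
| Stopping, mean 10%, moderate spread | 8.7% | 6.4% |
| Stopping, mean 10%, wide spread | 7.1% | 3.8% |
| Stopping, mean 5%, moderate spread | 4.3% | 3.3% |
| Stopping, mean 5%, wide spread | 3.6% | 2.0% |
| Stopping, mean 10%, all users alike | 10.1% | 10.2% |

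The last row shows that the decline requires users to differ.

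For time, without a user term and with the most failure-prone users also the slowest, the slope was −0.8% to −1.3% per use. A false finding of faster with use appeared in 9% to 20% of runs, against 3.5% to 4.0% without stopping and 2.5% nominal. At a correlation of 0.5 between slowness and failure risk (mean 10%, wide spread), the slope was −0.7% with 9% false findings. At zero correlation there was no slope (0.0% per use, 4.5% of runs), although the event decline remained (7.1% to 3.6%).

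With the slope estimated within user and stopping still in force, it was about zero, and false findings fell to 2.3% to 2.8%.

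**3. Why the within-user remedy does not carry over to events.** If a first failure ends use, a user's failure is always the last use. Anyone who reaches uses 4 to 7 had no failure in uses 1 to 3. In the 20%/2% case such users show 0% early and about 5% late with no true change, which is a false increase.

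**The case against.** The strongest objection is that 7.1 may concern one case only. The data it asks for at discontinuation include patient clinical data and the intubation record, which belong to a single procedure. Section 2.3.1 says that "the device can be quickly removed by releasing the safety strap connectors and taking the device off the bed" and has the user go on to intubate without it. The item in 2.3.3 on inability to intubate says much the same. Neither passage ends the user's later cases. Against that, 7.1 begins with active participation and remaining questionnaires, which fits a user at least as naturally. Both readings stand. On the per-case reading the main route to selective exit disappears, and only the discretionary withdrawals in 7.2 remain.

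A reader might infer from 7.2 that any adverse event removes a user. It does not: withdrawal is optional and tied to the participant's best interest. Patient anxiety or claustrophobia would not obviously meet that condition for a user.

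The plan also has partial safeguards. Users who stop stay in the study. Sections 9.4.2 and 9.4.3 say that all data points are analysed, and failing in the device is not plainly non-compliance. Experience is a covariate, withdrawal reasons are recorded, and events are broken down by user. These help, but experience removes only the measured part of the difference between users. Sections 9.3 and 9.4.2 also leave unclear whether a stopped user's procedures are kept.

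Finally, the fall in events is an expectation over calendar time. Section 9.4.2 specifies no trend test for it, and staggered user entry means that calendar time and use number differ. That limits the claim on events to how a decline would be interpreted.

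**Conclusion.** The point holds conditionally. If users leave device use because of failures or events, and if they differ in failure risk, a falling event rate by use number can arise without learning. A falling procedure time can also arise, but only if failure-prone users are slower as well. Section 2.3.3 expects a wide range of experience among users, so differences in risk are plausible, but the documents do not quantify them.

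The size rests on assumed rates: 8.0% to 4.3% over seven uses at 20% and 2%, but only 4.7% to 3.8% at 10% and 2%. It is much smaller if 7.1 applies per case. The distortion of the time slope is modest, at roughly 1% per use in the 15-user settings with a full link between slowness and failure.

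Two stronger readings are not supported. One is that the documents establish that users stop after a failure, so that any improvement would be an artefact; 7.1 is ambiguous, and real learning may also occur. The other is that the comparison of procedures with and without the device is undermined; patients are randomised, and this point does not touch that comparison. No shift in the median comfort or burden ratings has been shown either, only that the weighting of users could change.

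The point still merits a change, because the better analysis costs almost nothing.

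**What to change.** 1. Reconcile 7.1 with 2.3.1 and 2.3.3 on whether discontinuation applies to the procedure or to the user. The stopping criteria themselves are for the sponsor.
2. In 9.3, state that every procedure of a stopped or withdrawn user is kept, up to and including the one that led to stopping.
3. In 9.4.2, add a user effect to the time model, preferably fixed, so that the slope on prior uses is estimated within user.
4. For adverse events, do not use a within-user early-versus-late contrast. Report events per device use by use number, with the number of users still contributing and the exits with their reasons. Do not read a decline as learning without that table.
5. In 9.4.3, summarise comfort and burden with one value per user, such as each user's median rating, and include users who stopped. The last rating would not serve, because for a user who stopped it would tend to be the rating linked to the failed use.

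The cost is some wording, one extra table and slightly less precise trend estimates. User and device identifiers and withdrawal reasons are already collected, so no new data or patients are needed.
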